6.1.5 Vital Status Telephone Call

Conduct a vital status telephone call approximately 3 months after the subject's last study visit and approximately every 3 months thereafter for up to 5 years, death, or subject withdraws consent, whichever occurs first.

6.2 ORDER OF ASSESSMENTS OF SPECIFIC TESTS

SF-36:

- Must be administered **prior** to any other visit assessments on the day it is administered

6MWT:

- Must be performed 1-2 days **prior** to administration of study drug
- Should not be administered on Day 1 (i.e., the same day as NEOD001 administration)
- Blood samples must be collected for local (if applicable) and central laboratory assessments **before** the 6MWT is administered, if being performed on the same calendar day
- Collect BP and HR **pre-** and **post-**6MWT administration

ECGs:

- When ECGs are scheduled to be performed at the same visit as PK blood collection, the ECG must be done **first**
- For subject receiving chemotherapy, medications such as anti-emetics required for prophylaxis of emesis for the subsequent chemotherapy should be given **after** the ECG has been done

Chemotherapy and Routine Medications:

- Routine medications should not be administered in the **15 minutes after** the completion of the NEOD001 infusion
- If parenteral chemotherapy is administered on the same day as NEOD001, the chemotherapy must be administered **after** the 90-minute NEOD001 observation period
- Within 3 days before the first day of a new regimen of chemotherapy, conduct an unscheduled central laboratory collection (including hematology and chemistry, PT/INR, and PTT)

6.3 METHODS OF ASSESSMENT FOR SAFETY AND EFFICACY

6.3.1 Clinical Laboratory Evaluations

A central laboratory will be used for this study for analysis of hematology, chemistry (including amylase), PT/INR, PTT, troponin T, NT-proBNP, SFLC, SPEP, SIFE, UPEP, UIFE, urinalysis, and 24-hour urine assessment. Details for the processing of laboratory specimens will be provided in the Laboratory Manual. Local hematology, chemistry, and urinalysis laboratory results will be obtained at the Investigator's discretion for subject management when necessary for obtaining results on a more immediate basis. Local laboratory results should also be obtained and reviewed for a safety assessment prior to each administration of chemotherapy. Central and local pregnancy testing will be conducted as shown in [Table 1](#) and [Section 6](#). A positive urine pregnancy test (local laboratory) is to be confirmed with a serum pregnancy test (central laboratory). Results from local laboratory tests will not be collected in the eCRFs or the clinical database (*exception*: local laboratory pregnancy test results will be collected via an eCRF and in the clinical database).

In addition, a bioanalytical laboratory will be used for this study for the analysis of PK and anti-NEOD001 antibody samples, as well as for the storage of serum samples for future correlative testing ([Section 6.4](#)).

6.3.2 Vital Signs

Heart rate will be measured from the radial pulse counted manually or with an automatic BP monitor over at least 15 seconds and adjusted per minute.

Blood pressure (systolic and diastolic) will be measured after the subject has rested in a semi-recumbent position ≥ 5 minutes. Blood pressure measurements should be taken from the same arm throughout the study using an automated BP monitor that uses an oscillometric method. At Screening, BP measurements may be repeated twice. If there is a clinically important change in BP from the previous reading, measurements will be repeated immediately to confirm the change.

Respiratory rate will be measured over at least 15 seconds and adjusted per minute.

Measurement can be made using either oral or tympanic methods, but the method should be consistent throughout the study for a given subject.

6.3.3 Physical Examination

Any unfavorable findings considered by the Investigator as clinically significant, especially changes occurring between Screening and EOS, will be documented in the eCRF as an AE. Physical examinations must be performed by the Investigator or a medically qualified delegate.

All physical examinations should include weight and examination of the following: general appearance; head, ears, eyes, nose, and throat; neck; skin; cardiovascular system; respiratory system; abdominal system; and nervous system. The specific components of the physical examination will be as clinically indicated. However, at all time points the following should be assessed: macroglossia, submandibular nodes/fullness, adenopathy, ecchymoses, liver/spleen size (palpable +/-), ascites (+/-), and edema (which should be quantified on a scale of 0-4). The Screening physical examination will also include a measurement of height.

6.3.4 12-Lead ECGs

Measurements will be made in triplicate, 5 to 10 minutes apart and taken after the subject has rested in a supine position for ≥ 5 minutes. Heart rate, PQ/PR duration, QRS duration, QT duration, QTcF - Fridericia's correction formula, QTcB - Bazett's correction formula, and the Investigator's overall interpretation will be recorded. When ECGs are scheduled to be performed at the same time as PK blood collection, the ECG must be done before the PK blood collection.

6.3.5 Peripheral Neuropathy Assessment

The Peripheral Neuropathy Assessment form ([Appendix 5](#)), will be used to assess reflexes, sensation, and motor strength to determine a peripheral neuropathy score in subjects previously enrolled in Cohort C of Study NEOD001-001. A peripheral neuropathy grade based on the CTCAE scale ([Table 2](#)) will be determined at each assessment.

Table 2 Common Terminology Criteria for Adverse Events Grade 1-5 for Peripheral Neuropathy

	CTCAE Grade				
	1	2	3	4	5
Peripheral sensory neuropathy ^a	Asymptomatic; loss of deep tendon reflexes or paresthesia	Moderate symptoms; limiting instrumental ADL	Severe symptoms; limiting self-care ADL	Life-threatening consequences; urgent intervention indicated	Death

Abbreviations: ADL = activities of daily living (e.g., preparing meals, shopping for groceries or clothes, using the telephone, managing money, etc.); CTCAE = Common Terminology Criteria for Adverse Events.

^a Definition: a disorder characterized by inflammation or degeneration of the peripheral sensory nerves.

Source: [National Cancer Institute, 2009](#).

6.3.6 6-Minute Walk Test

The 6MWT will be assessed according to [Table 1](#). As part of the 6MWT, BP and HR will be collected pre- and post-6MWT administration. The 6MWT should not be administered on the same day that study drug is administered, but may be performed 1-2 days prior to the Day 1 visit at each required assessment. The SF-36 must be administered and clinical laboratory samples (local and central) must be drawn prior to administering the 6MWT, if being performed on the same calendar day.

Details regarding the requirements for proper administration of the 6MWT are described in a separate manual.

6.4 PHARMACOKINETIC AND IMMUNOGENICITY ASSESSMENTS

All subjects enrolled in the study will undergo sparse sampling for serum NEOD001 according to [Table 1](#). Serum NEOD001 concentrations from this study will be pooled with similar samples from other studies in a population PK analysis. Details will be provided in a separate document.

Serum anti-NEOD001 antibody levels will be measured according to [Table 1](#). An electrochemiluminescent assay will be used to detect serum anti-NEOD001 antibodies. Any screening positives will be run at increasing dilutions to and a titer determined (expressed as the reciprocal of the dilution that generates a positive response). Additionally, all positives will be run in a confirmatory assay to determine the response is specific to NEOD001.

Additional samples for anti-NEOD001 antibodies and serum NEOD001 should be collected if a significant toxicity is observed (e.g., an infusion reaction in the clinic, anaphylaxis, etc.) and if possible, should be collected while the acute symptoms persist.

Refer to the Laboratory Manual for additional details.

7 **ADVERSE EVENTS/SERIOUS ADVERSE EVENTS AND REPORTING**

7.1 **ADVERSE EVENTS—DEFINITION**

An AE is any untoward medical occurrence associated with the use of a drug in humans, whether or not considered drug related. An AE can therefore be any unfavorable and unintended sign (including a laboratory finding, for example), symptom, syndrome, or disease temporally associated with the use of a medicinal product, whether or not considered related to the medicinal product. Examples include:

- Any treatment-emergent signs and symptoms (events that are marked by a change from the subject's baseline/entry status [e.g., an increase in severity or frequency of preexisting abnormality or disorder])
- All reactions from study drug, abuse of drug, withdrawal phenomena, sensitivity, or toxicity to study drug
- Apparently unrelated illnesses
- Injury or accidents
- Exacerbations of the underlying disease (indication)
- Extensions or exacerbations or symptomatology, subjective events reported by the subject, new clinically significant abnormalities in clinical laboratory, physiological testing, or physical examination

The reporting period for AEs is from the time that the ICF is signed through 30 days after the last dose of study drug or last study visit, whichever is later. All AEs, whether or not related to the study drug, must be fully and completely documented in the eCRF and in the subject's medical notes. The following attributes must be assigned: description, dates of onset and resolution, severity, assessment of relatedness to study drug (either related or not related), and action taken. The Investigator may be asked to provide additional follow-up information.

In the event that a subject is withdrawn from the study because of an AE, it must be recorded in the eCRF. The subject should be followed and treated by the Investigator until the AE has resolved, stabilized, or a new chronic baseline has been established.

The Investigator must report all AEs. At each visit the Investigator will ask the subject a nonspecific question (e.g., "Have you noticed anything different since your last visit?") to assess whether any AEs have been experienced since the last report or visit. AEs will be identified and documented in the eCRF in appropriate medical terminology. The severity and the relationship to the study drug will be determined and reported in the eCRF (see Sections 7.2 and 7.3).

Note that any intermittent or as-needed ("PRN") use of medication (and specifically any newly prescribed medication) during the course of a study may indicate the occurrence of an AE that may need to be recorded on multiple eCRFs (e.g., AE and Concomitant Medication eCRFs).

7.2 ADVERSE EVENTS—SEVERITY RATING

AEs will be assessed according to CTCAE version 4.0 ([National Cancer Institute, 2009](#)). AEs that do not have a corresponding CTCAE term will be assessed according to their impact on the participant's ability to perform daily activities as listed below.

The severity of each AE should be characterized and then classified into one of five clearly defined categories as follows:

- **Mild (Grade 1):** the AE does not interfere in a significant manner with the subject's normal functioning level—it may be an annoyance
- **Moderate (Grade 2):** the AE produces some impairment of functioning, but is not hazardous to health—it is uncomfortable or an embarrassment
- **Severe (Grade 3):** the AE produces significant impairment of functioning or incapacitation and is a definite hazard to the subject's health
- **Life threatening (Grade 4):** Life threatening or disabling
- **Fatal (Grade 5):** Causes death of the participant

These five categories are based on the Investigator's clinical judgment, which in turn depends on consideration of various factors such as the subject's reports, the Investigator's observations, and the Investigator's prior experience. The severity of the AE should be recorded in the appropriate eCRF. The evaluation of severity is distinguished from the evaluation of "seriousness." A severe event might not meet the criteria for seriousness and a serious event might be evaluated as mild. For example, a subject might have a severe headache that does not require hospitalization and is consequently not serious; or a subject might have a mild myocardial infarction that requires hospitalization and is therefore serious.

7.3 ADVERSE EVENTS—CAUSALITY RATING

The causality of each AE should be assessed and classified by the Investigator as "related" or "not related." An event is considered related if there is "a reasonable possibility" that the event may have been caused by the product under investigation (i.e., there are facts, evidence, or arguments to suggest possible causation).

- **Related:** An Investigator should consider an AE related to the study drug if there is a reasonable possibility that the event may have been caused by the study drug.
- **Not Related:** An Investigator should consider an AE not related to the study drug if there is another reasonable explanation for the event to occur.

Consider the following when assessing causality:

- Temporal associations between the agent and the event

- Effect of dechallenge and/or rechallenge
- Compatibility with known class effect
- Known effects of concomitant medications
- Preexisting risk factors
- A plausible mechanism
- Concurrent illnesses

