5.6.1 Allowed Concomitant Medication/Therapy

The following are allowed during the study:

- Radiation therapy for the removal of local amyloid deposits
- Concomitant chemotherapy
 - The Investigator may prescribe chemotherapy as per standard of care
 - Particular care must be taken to accurately report chemotherapy administration, including missed or delayed doses, and dose reductions
 - If parenteral chemotherapy is administered on the same day as NEOD001, the chemotherapy must be administered after the 90-minute NEOD001 observation period
 - Within 3 days before the first day of a new regimen of chemotherapy, conduct an unscheduled central laboratory collection (including hematology, chemistry, PT/INR, and PTT)
 - Routine medications should not be administered in the 15 minutes after the completion of the NEOD001 infusion. Medications such as anti-emetics required for prophylaxis of emesis for the subsequent chemotherapy should be given after the ECG has been done.

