The reporting period for SAEs is the period from signing of the ICF through 30 days after the last administration of study drug or last study visit, whichever is later. SAEs reported to the Investigator outside of this reporting period will be reported to the Sponsor or its designee if, in the judgment of the Investigator, there is “a reasonable possibility” that the event may have been caused by the product.

All SAEs will continue to be followed until the end of the study or until such events have resolved or the Investigator, in conjunction with the Sponsor or its designee, deems them to be chronic or stable.

8 **STATISTICAL METHODS AND CONSIDERATIONS**

The final analyses will be based on all subject data collected through study discontinuation.

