10.3 ETHICS COMMITTEE APPROVAL

The Investigator at the site is responsible for obtaining IRB/IEC approval for the final protocol, the Sponsor-approved ICF, and any materials used to recruit subjects. Written approval of these documents must be obtained from the IRB/IEC before any subject is enrolled at a site.

The Principal Investigator is also responsible for the following interactions with the IRB/IEC:

- Obtaining IRB/IEC approval for any protocol amendments and ICF revisions before implementing the changes
- Providing the IRB/IEC with any required information before or during the study
- Submitting progress reports to the IRB/IEC, as required, during the conduct of the study; requesting re-review and approval of the study, as needed; providing copies of all IRB/IEC re-approvals and relevant communication to the Sponsor or its designee
- Notifying the IRB/IEC of all serious and unexpected AEs related to the study medication reported by the Sponsor or its designee, as required by local regulations

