9.2.5. Relationship to Study Drug as Assessed by Investigator

The crude and cumulative incidences of TEAEs by strongest relationship to study drug (Related/Not Related) will be summarized. At each level of subject summarization, a subject is classified according to the closest relationship to study drug if the subject reported 1 or more events. AEs with a missing relationship will be considered related for this summary. The following summaries will be presented:

- Subject incidence of related TEAEs by MedDRA SOC and PT
- Subject incidence of related CTCAE Grade 3 or higher TEAEs by MedDRA SOC and PT

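### Protocol 7.3 does not define Not Related as the complement of Related, so an event with both a plausible drug cause and another explanation can be coded either way

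*Protocol*

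**What the plan says.** Protocol 7.1 lists what must be recorded for every AE, including an "assessment of relatedness to study drug (either related or not related"). There is no third category.

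The lead sentence of Protocol 7.3 makes an event related on a reasonable possibility of drug causation, which it explains as facts, evidence or arguments pointing that way. Two bullets follow. For Related: "An Investigator should consider an AE related to the study drug if there is a reasonable possibility" of drug causation. For Not Related: "An Investigator should consider an AE not related to the study drug if there is another reasonable explanation for the event to occur". Then come seven factors to weigh. Some bear on the drug itself (timing, dechallenge or rechallenge, class effect, mechanism). Others bear on competing causes, such as "Known effects of concomitant medications", preexisting risk factors and concurrent illness. The factors carry no weights, and nothing says which bullet governs when both fit.

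Competing causes are built into this study. Every subject has AL amyloidosis, and Protocol 7.1 counts exacerbation of the underlying disease as an example of an AE. Under Protocol 5.6.1, "The Investigator may prescribe chemotherapy as per standard of care", even on the infusion day once the observation period is over.

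SAP 9.2.5 uses the rating directly, for example in "Subject incidence of related TEAEs by MedDRA SOC and PT", with crude and cumulative incidence. A missing relationship is counted as related; a completed rating is left as it stands.

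**The concern.** A binary rating needs definitions that exclude each other and together cover every case. These two do neither, because one asks about the drug and the other asks about everything else. Take a rise in creatinine between infusions in a subject with renal amyloidosis, or nausea some days after both NEOD001 and chemotherapy. The investigator may see a reasonable possibility of a drug effect and also another reasonable explanation. The protocol then gives two opposite instructions, and two sites could code the same event differently while both comply.

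Long-term safety is the primary objective and there is no control group, so no between-arm comparison can correct a misattributed event. Where the Not Related bullet is followed in the overlap, the error goes one way: suspected reactions leave the related tables.

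**Working it through.** The documents state no figure on this point, so there is none to reproduce. The check is one of logic, followed by a trace of where the rating is used.

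**Step 1. The two definitions.** Let R mean that there is a reasonable possibility that NEOD001 caused the event, and A that there is another reasonable explanation. The bullets in Protocol 7.3 say: Related if R; Not Related if A. For a clean binary scale, A would have to be equivalent to not-R.

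| R | A | Related bullet met | Not Related bullet met | Result |
|---|---|---|---|---|
| yes | no | yes | no | Related |
| no | yes | no | yes | Not Related |
| yes | yes | yes | yes | both met, no tie-break |
| no | no | no | no | neither met |

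Two of the four combinations are not resolved by the bullets. The third row is the one that matters here, because the disease and permitted chemotherapy are both sources of A.

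**Step 2. Outputs that use the rating.**
- SAP 9.2: the listing of related AEs (marked related, or relationship missing).
- SAP 9.2.2: three rows of the overall summary (treatment-related, treatment-related serious, and treatment-related Grade 3 or higher TEAEs).
- SAP 9.2.5: related TEAEs and related Grade 3 or higher TEAEs, crude and cumulative.
- SAP 9.2.7: serious related TEAEs.

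The only recoding is of missing relationships. An overlap event coded Not Related has a completed field, so that rule does not recover it.

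**Step 3. Outputs and processes that do not use it.**
- All-causality TEAE, severity, dosing-change, serious, fatal and withdrawal tables (SAP 9.2.3, 9.2.4, 9.2.6 to 9.2.8), apart from the serious related table.
- TEAEs starting on an infusion day, events answered yes to the separate infusion-associated question, and the anaphylactic reaction query (SAP 9.2.9).
- Recording of all AEs whether or not related (Protocol 7.1), and reporting of all in-period SAEs to the sponsor within 24 hours (Protocol 7.4.4).

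**Step 4. Size.** Let f be the share of events with R that also have A, and g the share of those that sites code Not Related. The share of suspected reactions missing from the related tables is f × g. The documents give neither f nor g, and no rate of related events or of chemotherapy use in this study. The product is therefore bounded only by 0 and 1, and no estimate is possible.

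**The case against.** The strongest reply is that 7.3 has one standard, stated first and repeated in the Related bullet: reasonable possibility. On a binary scale an investigator can take that sentence as governing, which also settles the case where neither bullet is met. Another reasonable explanation can be read as one that accounts for the event instead of the drug, and the factors listed suggest weighing rather than an automatic rule. This is a sensible reading, and some sites may use it. It is not the only compliant one: both bullets are framed as the same instruction to the investigator, neither is subordinated to the other, and nothing says that the lead sentence overrides the Not Related bullet.

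The objection on reach largely stands. A reader might infer that relatedness drives most safety actions, but the documents do not support that:
- SAE reporting covers "the period from signing of the ICF through 30 days after the last administration of study drug or last study visit", whichever is later, without regard to causality. For SAEs after that period, Protocol 7.4.4 uses the reasonable-possibility test itself.
- The ethics committee duty in Protocol 10.3, "Notifying the IRB/IEC of all serious and unexpected AEs related to the study medication", continues by limiting it to events reported by the sponsor or its designee, so it does not rest on the site's code alone.
- Dose reduction (Protocol 5.4.3) turns on consultation with the Medical Monitor, and suspected infusion reactions (5.4.2) are handled on suspicion.

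A reader might also infer that nearly every event could be coded Not Related, or assume that, say, 50% to 90% of suspected reactions are lost. Any such share is put in and comes straight back out; it is not evidence. The common parent-study TEAEs in Protocol 1.3.2 do not supply it either: they were listed regardless of relationship, from a study of single-agent NEOD001, and show nothing about miscoding.

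**Conclusion.** The definitions in Protocol 7.3 are wrong as written. They overlap and leave a gap on a forced binary scale, with no stated precedence, so an event plausibly due to NEOD001 and also to AL amyloidosis or chemotherapy can be coded Not Related. This follows from the wording and needs no numerical assumption.

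The consequence is confined mainly to the related-AE listing and the related, related Grade 3 or higher and related serious TEAE summaries. In an uncontrolled safety study those are worth protecting, but the all-causality results are intact. How many events are affected is unknown, and the documents do not show that any event was miscoded. I make no claim about ratings made in the parent study, whose protocol is not among the documents.

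**What to change.** Reword the second bullet of Protocol 7.3 along these lines: *Not Related: there is no reasonable possibility that the event was caused by the study drug.* Add a sentence saying that another possible explanation, such as AL amyloidosis, chemotherapy or other medication, does not by itself make an event Not Related. The categories then exclude each other, cover every case and agree with the section's own lead sentence. Any eCRF completion instructions should match; they are not among the documents, so their present content is unknown.

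The cost is a sentence or two. The count of related events may rise, by an amount that cannot be predicted. No dose or procedure changes.

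SAP Section 11 records that the NEOD001 program was discontinued, so ratings may already be final. In that case, disclose in the clinical study report that the two definitions overlapped, present the related-event tables with that caveat, and base safety conclusions on the all-causality tables.
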